#### 9.5.7 Visit 7: 28 days post V6 (+14 days)

#### Applicable for all sub-groups

1. Check Inclusion/ exclusion criteria are still valid

2. Review eDiary or paper diary for AEs/SAEs and prescription medicine since the last visit

3. Record and report any AEs/SAEs that have occurred since the last visit.

- 4. Measure and record axillary temperature
- 5. Blood sampling: obtain up to 6 mls

6. Collect Mucosal Lining Fluid (MLF) using synthetic absorptive matrices (SAM)

7. Administer 0.5ml MMR by intra-muscular injection into the upper right antero-lateral thigh record in source document and in red book

8. Administer 0.5ml Men C by intra-muscular injection into the lower right antero-lateral thigh record in source document and in red book.

9. Administer 0.5ml dose of 4CMenB by intra-muscular injection into the left antero-lateral thigh record site and time of vaccinations and batch number in source document and in red book

10. Observe the participant for 15 minutes after vaccination for any significant acute reactions, with appropriate medical treatment readily available in case of anaphylactic reaction. Any AEs occurring during the observation period should be recorded in the source document

11. Instruct parent/legal guardians to contact the study team immediately should they manifest any signs/ symptoms they perceive as serious or if the child is admitted to the hospital.

12. Complete paperwork in case of no direct data entry and enter onto database

13. Give letter of "end of the study" to the parents

#### 9.6 Blood sampling

Blood sampling will be carried out in line with SOPs. A local anaesthetic cream will be applied for an appropriate period of time prior to each venepuncture. The maximum blood volumes requested for each sample are in accordance with the NIHR Medicines for Children Research Network[57], that states that "per individual, the trial-related blood loss should not exceed **3%** of the total blood volume during a period of **four weeks** and should **not exceed 1% at any single time**. **The total volume of blood is estimated at 80 to 90 ml/kg body weight**"; **3% is 2.7 ml blood per kg body weight** considering a total estimated volume of 90 ml/kg body weight.

For the calculations, we considered the WHO centile curves for girls and boys on the 5th centile as representative of the smallest participant and the visit schedule one-month period. Based on these estimates a maximum of 4 ml of blood could be safely obtained during blood visits for laboratory analysis in participants up to 6 months of age (V1 (baseline), and V5), and a maximum of 6 mls in participants at 12 and 13 months of age (V7, V8). Blood volumes and assays for each group are shown in **table 3** 

If the initial attempt at venepuncture is unsuccessful, verbal consent will be sought from the parents for a further attempt at that visit. No more than two attempts at venepuncture will be made.

#### 9.7 Mucosal lining fluid sampling

Nasal absorption is performed by manoeuvring a strip of synthetic absorptive matrices (SAM) up the lumen of the nostril, avoiding rubbing against the nasal mucosa. The outside of the nose is then pressed with a finger to cause apposition of the SAM against the mucosa. The procedure may tickle slightly but is painless, and MLF can be obtained even from non-inflamed noses at frequent intervals, without the need for local anaesthetic. Imperial College London has performed successful studies with nasal strips in adults after nasal allergen challenge (NAC), in babies and in young children, showing the applicability of this procedure to this age group. There is minimal protein binding to the SAM strip, and fluid can be eluted by spin filtration. High levels of mediators of inflammation can then be measured in the MLF: higher than detectable by nasal lavage.

#### 9.8 Recording symptoms electronic diary card (RedCap)

The parents of participants will be asked to maintain a diary card detailing all (solicited and unsolicited) reactions in the 7 days following the 2, 4, and 12 months vaccinations (V1, V3 & V6), as well as prescription medications that are given in the 28 days that follow these time-points.

The parents will be issued an electronic diary (using RedCap). In case the parents cannot access the electronic diary, they can record the requested information on a paper diary, which has the same exact structure as the ediary.

The electronic diary will include space to record the following reactions at these time points:

1. Local reactions (erythema, induration and swelling) and tenderness. Parents will be issued with a ruler to measure any local reactions, and tenderness severity will be graded as shown in **table 2** 

2. **Temperature**. Parents will be asked to record axillary temperatures at four and eight hours post vaccine and once daily from then on using the digital thermometer provided. The axillary temperature will also be measured if, at any time, the parent feels that the child may have developed a fever.

3. **Solicited systemic reactions**. The electronic and paper diary will include a grid for parents to record the presence or absence of a number of systemic symptoms that have previously been reported following vaccination: change in eating habits, drowsiness, irritability, and change in activity, vomiting and diarrhoea. Parents will grade severity according to the descriptions in **Table 2**.

4. **Unsolicited adverse events**. There will be space to record any other symptoms that occur in the 7days post vaccination.

The electronic or paper diary will be reviewed at each post vaccination visit. If symptoms persist after 7 days, an end-date should be entered if available. If concomitant medication persists beyond day 28, an end date will be entered if available. Parents/ legal guardians will be provided with a 24-hour phone number to access a member of the study team should they require urgent advice

	Grading of severity				
Solicited Reactions	Mild (1)	Moderate (2)	Severe (3)		
Tenderness	Minor reaction to touch	Cries/protests on touch	Cries when limb is moved / spontaneously painful		
Change in feeding habit	Feeding less than usual / no effect on normal activity	Feeding less than usual / interferes with normal activity	Not feeding at all		
Drowsiness	Drowsiness easily tolerated	Drowsiness that interferes with normal	Drowsiness that prevents normal activity		

Table 2: Grading local and systemic reactions

		activity	
Reduction in normal activity	Less interested in surroundings, toys etc	No interest in above and sleeping through feeds	Sleeping most of the time
Irritability/fussiness	Crying more than usual / no effect on normal activity	Crying more than usual / interferes with normal activity	Crying that cannot be comforted / prevents normal activity
Vomiting	1-2 episodes without interfering with routine	Several episodes & cannot keep any food down	Frequent episodes & taking nothing by mouth
Diarrhoea	More loose stools than usual	Frequent runny stools without much solid material	Multiple liquid stools without much solid material

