#### Adverse events after pertussis immunisation - aP and wP

The nature of local and systemic reactions following aP and wP are similar to those recognised for other childhood vaccines. These include redness, swelling and pain in the limb where the vaccine was given (local reactions) and fever, irritability and crying (systemic reactions). The incidence of such reactions is higher after wP than after immunisation with aP[26].

More significant reactions such as febrile convulsions and hypotonic-hypo responsive episodes (HHE) are rare. Febrile convulsions are relatively common in the setting of infectious causes of fever but can more rarely follow fever caused by immunisation. The incidence of febrile convulsions after immunisation has been estimated at 1/200,000 and 1/16,000 immunisations for aP and wP vaccines respectively[39]. Hypotonic-hyporesponsive episodes (also called "floppy baby") involve the sudden onset of limpness, reduced responsiveness and looking pale usually within 48 hours of receipt of immunisation. Although these can be experienced by parents as frightening, the children recover spontaneously and no sequelae were reported in children with no underlying neurological conditions [40, 41]. These episodes are rare and can occur after any childhood vaccine. A recent Cochrane review demonstrated that HHE can occur after the administration of aP or wP vaccines, although they are more likely to happen after wP[26]. The estimated incidence for HHE is of ~1/1,600-7,000 versus ~1/400-1,700 for aP versus wP vaccines[39]. Typically, HHE occur with the first immunisation dose and do not recur with subsequent doses. They are not a contra-indication to further doses of vaccine.

As for all vaccines, there is a very small chance of a severe allergic reaction to both aP and wP vaccines.

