#### Then:

1.Administer 0.5ml DTaP-IPV-Hib-Hep B by intra-muscular injection into the upper right anterolateral thigh (aP group) record in source document and in red book

2. Administer 0.5ml DTwP-Hib-Hep B by intra-muscular injection into the upper right antero-lateral thigh (wP group), record in source document and in red book

3. Administer 0.5ml PCV by intra-muscular injection into the upper left antero-lateral thigh record in source document and in red book (both aP and wP groups)

4. Administer 0.5ml IPV by intra-muscular injection into the lower left antero-lateral thigh (wP group), record in source document and in red book

5. Administer Rotavirus vaccine oral drops

6. Issue eDiary login details to parent (or give paper diary), ask parent to login and change password. Demonstrate eDiary (or paper diary) to parents for recording AEs and paracetamol +/-ibuprofen use and check understanding.

7. Issue a digital thermometer and ruler. Explain how to measure and record temperature, local and systemic reactions, AEs (for 7 days post any vaccination) and concomitant medications (for 28 days post vaccination).

8. Issue the parents/ legal guardian with a continuous temperature-monitoring device together with instructions. Fit on the child and demonstrate how to fit, check function and remove device

9. Observe the participant for 15 minutes (or for 30 minutes for participants who have received Comvac5) after vaccination for any significant acute reactions, with appropriate medical treatment readily available in case of anaphylactic reaction. Any AEs occurring during the observation period should be recorded in the source document

10.Issue (only if parent's do not have any) and provide instructions on the use of paracetamol prophylaxis to those whose infant is randomised to receive wP

11. Instruct parent/legal guardians to contact the study team immediately should the infant manifest any signs/ symptoms they perceive as serious or if the infant is admitted to the hospital.

12. Leave with parents/guardians anaesthetic cream (unless spray is to be used), dressing pads and instructions for blood test visit (V5, at 5months).

13. Schedule next visit

14. Study staff complete red book, paperwork in case of no direct data entry and enter onto database

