## 13.2.2 Serious adverse events (SAE)

## a) Definition:

A SAE is any untoward medical occurrence or affect that at any dose:

-results in death;

-is life threatening (at the time of the event);

-requires hospitalisation or prolongation of existing inpatients' hospitalisation;

-results in persistent or significant disability or incapacity;

-is a congenital anomaly or birth defect; or

-any other important medical event that did not result in any of the outcomes listed above due to medical or surgical intervention but could have been, based upon appropriate judgement by the investigator.

A hospital admission for an elective procedure will not be considered as a SAE.

Other 'important medical events' may also be considered serious if they jeopardise the participant or require an intervention to prevent one of the above consequences. For this specific case, hypotonic hyporesponsive episodes, even if they do not require hospitalisation, would be considered a medically relevant event and reported as an SAE if occuring within 48hours after immunisation. Although this event is considered rare it has been described to occur more commonly after wP vaccination compared to aP. Pertussis confirmed cases would be reported as an SAE, due to a reduced primary schedule (2+1) when compared with the current UK schedule (3+0).

NOTE: The term "life-threatening" in the definition of "serious" refers to an event in which the participant was at risk of death at the time of the event; it does not refer to an event, which hypothetically might have caused death if it were more severe.

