## 13.3 Adverse events, serious adverse events and suspected unexpected serious adverse reactions: Procedures

#### 13.3.1. Procedures for Recording Adverse Events:

For the first 7 days after immunisation at visits 1, 3 and 6 (Day 0 to Day 7), all AEs observed by the study team or reported by the participant's parent/ legal guardian, whether or not attributed to study medication, will be recorded in the RedCap or paper diary. Reactions occurring in the first 7 days after immunisation (including day of immunisation) will be divided up into: solicited reactions, which will be considered related to study vaccine unless stated otherwise; and unsolicited adverse events, which will be assessed for relatedness and graded for severity by a medically qualified member of the study team. There will be space in the electronic or paper diary to record the end date of adverse events that continue beyond Day 7. The RedCap system will allow review by clinical staff of grade 3 AEs in real-time.

Medical events not considered SAEs that occur 7 days after immunisation do not need to be recorded. Because of the possibility that medication may interfere with the evolution of an immune response, the details of any prescription medication that is given within 28 days following the 2, 4 or 12 month vaccinations will be recorded on the eDiary or paper diary. Information on paracetamol/ ibuprofen use within 72 hours prior to immunisation and in the 7 days following immunisation will be specifically asked for.

AEs will be recorded using the following guidance:

• Pre-existing medical conditions (present before start of the AE collection period) are considered "concurrent medical conditions" and should not be recorded as AEs. However, if the participant experiences a worsening or complication of such a condition, the

worsening or complication should be recorded as an AE. Investigators should ensure that the AE term recorded captures the change in the condition (e.g. "worsening of")

 Each AE should be recorded to represent a single diagnosis. Accompanying signs or symptoms (including abnormal laboratory values) should not be recorded as additional AEs.

All AEs that are considered related and result in a participant's withdrawal from the study or are present at the end of the study should be followed up until the end of symptoms or the condition becomes stable.

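### Hypotonic-hyporesponsive episodes (HHE) are a protocol-defined SAE, but no diary item asks about them, so a brief episode reaches the team only by unprompted parental report.

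*Protocol*

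**What the plan says.** Section 13.2.2 of the protocol singles the event out: "hypotonic hyporesponsive episodes, even if they do not require hospitalisation, would be considered a medically relevant event and reported as an SAE", provided that it falls within 48 hours of immunisation. The reason follows at once: "Although this event is considered rare it has been described to occur more commonly after wP vaccination compared to aP".

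The background section on adverse events after pertussis immunisation describes the presentation. The episodes "involve the sudden onset of limpness, reduced responsiveness and looking pale usually within 48 hours of receipt of immunisation". It adds that children recover spontaneously, that parents can find an episode frightening, and that it typically follows the first dose.

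Section 9.8 sets out the diary. The solicited systemic symptoms are "change in eating habits, drowsiness, irritability, and change in activity, vomiting and diarrhoea", graded by parents with Table 2. There is also free space for other symptoms in the 7 days after vaccination, a 24-hour telephone number, and diary review at each post-vaccination visit. A paper diary is allowed.

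Section 13.3.1 says: "The RedCap system will allow review by clinical staff of grade 3 AEs in real-time". Unsolicited events are graded by a medically qualified member of the study team, not by the parent.

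The visit instructions, for example in section 9.5.1, tell parents to make contact immediately for "any signs/ symptoms they perceive as serious" or if the infant is admitted to hospital. Section 9.4 states that neither families nor staff are blinded.

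**The concern.** The protocol creates a special SAE but describes no prompted way of detecting it. Section 13.2.2 exists for the episode that does not lead to admission, so the admission trigger in the contact instruction cannot catch that case. What remains is the parent's judgement that something was serious, or an entry in the free-text field. No real-time route is described for ungraded free text or for the paper diary.

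Two things are at stake. The first is timing: the 24-hour report to the PI (section 13.3.2) and the 7-day notice of serious adverse reactions to the DSMC chair (section 13.5) can start only once the team knows of the event. The second is classification: SAE status turns on a 48-hour window, and the protocol does not ask for time of onset in free text. An episode found at a later visit would then be classified on parental recall.

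**Working it through.** **Step 1. Set the features of HHE against the diary.**

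| Feature in the background section | Nearest item in section 9.8 / Table 2 | Prompted? |
|---|---|---|
| Sudden limpness | None | No |
| Looking pale | None | No |
| Reduced responsiveness | Drowsiness; reduction in normal activity | Partly, but the severe grades describe sustained states such as sleeping for most of the time |

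A brief episode with full recovery need not score as severe on any item.

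**Step 2. Trace the routes to the study team.**

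- Grade 3 entry in RedCap: real-time review is named.
- Free text in RedCap: no parent grade, and no real-time review is named.
- Paper diary: no real-time route is described.
- Telephone: open at all hours, but it rests on the parent's perception.
- Next visit: the diary and AEs/SAEs are reviewed. V2 and V4 fall 7-14 days after V1 and V3 (sections 9.5.2 and 9.5.4). V7 falls 28 days after V6 with a 14-day allowance, so 28-42 days (section 9.5.7).

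The longer gap follows only the 12-month dose, which is the aP-containing vaccine in both arms (section 7.2, Table 1). After a wP dose the gap is 7-14 days.

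**Step 3. How likely is a case?**

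Inputs: HHE incidence of about 1/400 to 1/1,700 for wP and 1/1,600 to 1/7,000 for aP (background section); 57 infants per arm (section 7.1.2); two priming doses, so 57 × 2 = 114 doses per arm. The background section states no denominator for these rates; I take them as per dose. I also assume full enrolment, no dropout and independent doses with equal risk.

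Formulas: expected cases = n × p; P(at least one) = 1 − (1 − p)^n.

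| Doses | p | Expected | P(at least one) |
|---|---|---|---|
| wP priming, 114 | 1/1,700 | 0.07 | 6.5% |
| wP priming, 114 | 1/400 | 0.29 | 24.8% |
| aP priming, 114 | 1/7,000 | 0.02 | 1.6% |
| aP priming, 114 | 1/1,600 | 0.07 | 6.9% |

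If only first doses carry the quoted rate (57 doses), wP gives 1 − (1 − 1/1,700)^57 = 3.3% to 1 − (1 − 1/400)^57 = 13.3%.

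Over all pertussis doses in the trial there are 114 wP doses and 114 + 114 = 228 aP doses, the second 114 being the booster in both arms:

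- Low: 1 − (1 − 1/1,700)^114 × (1 − 1/7,000)^228 = 9.5%, with 114/1,700 + 228/7,000 = 0.10 expected cases.
- High: 1 − (1 − 1/400)^114 × (1 − 1/1,600)^228 = 34.8%, with 114/400 + 228/1,600 = 0.43 expected cases.

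The plan gives no figure of its own for this point, so there is none to reproduce.

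**The case against.** The case on the other side is substantial.

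- Several routes exist, in both arms: free text, a 24-hour line, an instruction to call at each visit, and an AE/SAE check at each follow-up visit. The protocol itself says that parents can find HHE frightening, so many would call. This stands: the gap is reliance on spontaneous report, not the absence of a route.
- A reader might infer that the system alerts staff to grade 3 entries and to nothing else. Section 13.3.1 says that it allows review of such entries in real time. It describes no alert and does not exclude other review.
- A reader might infer that cases would surface mainly in the wP arm because those families are warned. No section describes a warning about HHE for wP families alone. Consent covers known side effects and risks for every family (section 9.3) and comes before the allocation envelope is opened (section 9.5.1). After allocation, wP families alone receive the paracetamol instruction at V1 and V3 and the longer observation at V1. With open allocation this makes unequal reporting possible, but it does not show it.
- Confirmed pertussis is also a protocol-specific SAE without a diary item. The parallel is weak: that event is defined by being confirmed, whereas HHE may be brief, resolve at home and leave no record.
- The diary template, parent information and other safety documents are not shown and may already hold such a prompt. This stands as a limit on the point.

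**Conclusion.** The point holds as a mismatch within the protocol text. HHE is a named SAE with a 48-hour window, but it is not a solicited item, and the only real-time review named is for grade 3 events. A brief, self-resolving episode that a parent neither telephones in nor scores as severe may wait 7-14 days after a priming dose, or 28-42 days after the booster.

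The size is modest. With the rates taken as per dose, the chance of at least one case in the priming series is about 6-25% with wP (about 3-13% if only first doses carry the risk) and about 2-7% with aP. Even at the highest rates fewer than 0.5 cases are expected in the whole trial, so zero is the most likely count. A reader might go further and say that the gap threatens the comparison of HHE between arms. With 57 infants per arm that comparison is not informative in any case. What matters is that a single SAE, if it occurs, is recognised promptly and timed correctly. Nothing in the primary immunogenicity analysis is affected.

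**What to change.** Add one yes/no item to the electronic and paper diaries for days 0-2 after the 2-, 4- and 12-month doses, worded identically in both arms: sudden limpness, reduced responsiveness or pallor, with date and time of onset. In section 13.3.1, give any yes the same real-time review as a grade 3 entry, and ask families on the paper diary to telephone it in. If the diary template already has such a prompt, it is enough to say so in section 9.8.

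The cost is one diary line, one review rule and a few false alarms, since pallor or sleepiness after vaccination will sometimes be ticked. The change concerns data capture only and leaves clinical care as it is.

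If dosing is already complete, which is possible given the extension to June 2024 in Appendix D, the item can no longer help. The trial report should then state that HHE was captured by unprompted report only, so that a count of zero is read accordingly.

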## 9.9 Concomitant Medication

Prescription medication taken within 28 days following the 2 or 4 month and 12 month vaccinations will be recorded by parents on the electronic diary system (or paper diary), together with the reason for starting it, and the start and stop date if applicable. Ibuprofen and paracetamol use within 72 hours prior to immunisation and within 7 days following immunisation at these visits will be recorded. Antibiotic use in the 7 days preceding a visit will be recorded. Electronic (or paper) diary entries will be reviewed with the clinical staff at the next visit.

